### **Outcomes:**

[figure not shown]
Primary = medication adherence, A1c, blood pressure, low density lipoprotein cholesterol

Secondary = quality of life, self-efficacy

## Study Design

We will compare usual care to viewing an educational DVD including peer storytelling and a 6-month telephone-delivered peer coaching intervention. We propose to use an RCT design because we aim to test the effectiveness of the intervention on medication adherence and A1c, blood pressure and cholesterol.

The trial will be cluster-randomized to reflect the clustering of patients within tightly knit small rural communities. People talk frequently within these communities, and if two participants from the same town are in different trial arms and compare notes, this could change their behavior and threaten the validity of the study. Each of the anticipated 80-100 towns will therefore be group-randomized in blocks to avoid contamination across trial arms. We considered using physician practices as clusters, but we have learned that it is common for different family members to attend different practices many miles from home.

## **Study population**

The priority population for this project lives in rural counties located in the Alabama Black Belt, which is heavily burdened by diabetes and lacking in primary health care providers and resources.

### ***Inclusion Criteria***

Individuals who meet the following criteria will be eligible to participate in the study.

- Adults aged 18 or older
- Have been told by a doctor or nurse that they have diabetes
- Take oral medications for their diabetes
- Medication non-adherent
- Has a primary care doctor

### ***Exclusion Criteria***

- Not community-dwelling
- Less than 18 years of age
- Are pregnant
- Have end-stage medical conditions with limited life expectancy
- Do not have a primary care doctor
- Expect to move out of the area in the next 6 months
- Cannot speak English

## Study Outcomes and Measures

### Primary Outcomes

The primary outcomes will include medication adherence. We will use the Morisky scale, which has been widely used and corresponds well to physiologic measures, but self-report is subject to recall and social desirability biases. Because of all the shortcomings related to assessment of adherence, we will also assess the result of improved adherence: better risk factor control. Three physiologic measures, A1c, blood pressure and LDL-cholesterol make up the “*A-B-C’s*” of diabetes care, which will be assessed here. The “*A-B-C’s*” of diabetes are a central focus of diabetes education, and the intervention will address medication adherence to control all three risk factors.

### Secondary Outcomes

Secondary outcomes will be health-related quality of life and self-efficacy. *Quality of life* will be assessed through the validated Short-Form 12 (SF-12), a generic measure of health-related quality of life. We will assess diabetes-specific quality of life using the validated Diabetes Distress Scale. *Self-efficacy* in taking medications will be assessed using the Self-efficacy for Appropriate Medication Use and the Perceived Diabetes Self-Management Scale, which is associated with A1c.

We will also assess the number of physician office visits, hospital stays and emergency visits in the previous 6 months, but do not anticipate that the short duration of the study will be able to detect significant differences between trial arms. Nevertheless, we will collect these data to build toward future longer term intervention studies. In addition, during the in-home visit we will transcribe the name and dose of all diabetes, blood pressure and lipid medications at baseline and follow-up to detect whether regimens have been intensified as a result of exposure to the interventions.

### Additional Measures

To understand the pathways through which the intervention is exerting its effects, we will collect additional measures guided by our conceptual framework. Our initial list of candidate measures is organized by theoretical construct and the Corbin and Strauss framework. Where available, we have selected validated scales that have been tested in low-literacy populations.

Patient characteristics	Age, sex, race, ethnicity, income, education, internet use, smoking status
	Duration of diabetes
	Insulin use
	Comorbidities
Health Care Access	Health insurance
	Distance from home to doctor
	Access to care question
Medication Adherence	4-item Morisky Medication Adherence Scale
Barriers to medication adherence	Medication Barriers Scale
Diabetes distress	Diabetes Distress Scale (DDS4)
Diabetes knowledge	Spoken Knowledge in Low Literacy in Diabetes (SKILLD)
Depressive Symptoms	Personal Health questionnaire (PHQ8)
Health related quality of life	Short-Form 12 (SF12)
Perceived stress	Perceived Stress Scale (PSS-10)

Self Efficacy	Self Efficacy for Appropriate Medication Use Scale (SEAMS)
	Perceived Diabetes Self-Management Scale (PDSMS)
Self care behaviors	Diet questions
	Exercise Questions
Social Support	Chronic Illness Resources Survey
	Social Support Scale
Trust	Trust in medical researchers
Numeracy	Subjective Numeracy Scale (SNS)

## Process Measures

A careful assessment of intervention implementation can provide insights into which aspects of the intervention were particularly effective. We will use cell phones provided by the study to track the frequency and amount of time spent on coaching sessions, as well as how closely they were implemented on schedule. Additional process measures will come from the peer coach Workbooks for each participant. These will include notes from each session as well as data entered for specific activities. We provide a chapter from our current trial’s Peer Coach Workbook in the Appendix to give a general idea of how these workbooks capture process data. We also monitor intervention implementation on an ongoing basis through weekly teleconferences with peer coaches, and weekly outreach to each peer coach individually throughout the intervention period. We provide updates on the progress of the study, collaboratively troubleshoot problems, and provide ongoing advice, which often stems from other peers or the community coordinators. We also address specific concerns with the help of our community coordinators (e.g., finding participants whose telephone numbers have changed).

## Randomization

We will use a block randomization scheme for randomization. The units of randomization are towns identified by zip codes. We will group towns by size (small and not small) within each of the 4 regions, resulting in 8 strata. We will balance the strata so that at least 3 towns are in each stratum. With 55 towns in the two regions participating in the 400-member Encourage study, we conservatively estimate at 80-100 towns with the addition of two more regions, providing sufficient sample as well as clusters

As participants agree to enroll and provide informed consent, they will be randomized as a representative of their town. That is, the first member of a given town will determine the randomization status of that town. All subsequent town residents will be placed into the same trial arm as the first participant from that town. Informed consent will be obtained from all participants. We will obtain verbal consent over the telephone at the time of the baseline telephone interview. Formal written informed consent will be obtained at the time of the in-home data collection visit. Participants will view a video providing information about the study with the opportunity to call a toll-free number for questions.

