**Technical merit. Project Overview.** We will build on our ongoing partnerships with people living in Alabama's Black Belt, learning together how to improve outcomes for individuals with diabetes. In the first year of the study we will conduct focus groups with people with diabetes and medication nonadherence to learn more about their beliefs and attitudes toward living with diabetes and the medications used to treat the disease. Using this information and working within the Corbin and Strauss framework, we will collaboratively create DVDs of peer storytelling integrated into a diabetes education experience, and the peer coaching protocol, drawing on Social Cognitive Theory and Adult Learning Theory. We will pilot test the intervention, and we will implement the randomized controlled trial (RCT) comparing the effectiveness of the intervention with usual care. In years 2 and 3, we will recruit 500 individuals with diabetes who report medication nonadherence, group randomize them to one of the 2 trial arms, and collect baseline and follow-up data 6 months later. Control patients will receive comprehensive diabetes education on conclusion of the 6 month period. During all 3 years, we will also work with community coalitions in our partnering communities to obtain ongoing input, share knowledge of community resources, create a resource bank website to facilitate the peer coaches' work, and plan for dissemination of the interventions.

Figure 3. Partnering communities in the Alabama Black Belt: North ([name]), Western ([name]), South Central ([name]).

**The setting and our partnership.** Booker T. Washington described the Black Belt as “a part of the country which was distinguished by the colour of the soil. The part of the country possessing this thick, dark, and naturally rich soil was, of course, the part of the South where the slaves were most profitable, and consequently they were taken there in the largest numbers. Later and especially since the (Civil) war, the term seems to be used wholly in a political sense—that is, to designate the counties where the black people outnumber the white.” The Black Belt runs in an arc across central Texas up to Maryland. In Alabama, it is a 200-mile wide belt across the southern half of the state (Figure 3).

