### Power Calculations and Sample Size

This study is powered to detect clinically meaningful differences in changes in medication adherence, A1c, blood pressure and LDL-cholesterol between either of the intervention arms compared with the usual care arm. The secondary outcomes are based on surveys (disease acceptance, quality of life). To consider the clustering of patients within town, we used a variance inflation factor  $D = [1 + \rho(m - 1)]$ , where  $m$  is the number of participants per community and  $\rho$  is the intra-class correlation (ICC). We conservatively estimate that we will have at least 80 clusters, corresponding to an average of 6-8 participants per cluster, with ICC=0.01 and 0.05 yielding  $D=1.084$  and  $1.419$ , respectively. Dividing the sample size per group  $N$  by  $D$  gives  $N_{\text{EFF}}$ , the effective sample size. In the Encourage study, those reporting nonadherence at baseline demonstrated ICCs in the range of 0.001-0.015 for most measures. To be conservative because we include new communities, we present power calculations for ICC=0.01-0.05. We observed 20% attrition over one year in the Encourage study and although attrition is likely to be lower over 6 months, we assume 20% attrition here, leaving 200 participants per group. Table 7 displays the detectable differences in adherence proportions and the difference in mean changes between groups detectable with 80% power using 2-sided  $X^2$  and t-tests with  $\alpha=0.05$ . We used variances based on the Encourage sample reporting nonadherence at baseline. We hypothesize that the intervention will result in improved medication adherence. Because eligibility requires low adherence at baseline, we expect low acceptance at baseline. Starting with low baseline values by design eliminates ceiling effects and allows us to reasonably anticipate large changes in the intervention groups and only modest changes in the control arm, as was seen in a storytelling intervention directed at blood pressure. For  $N=200$  per group, the difference in rates of medication adherence treated as a binary outcome detectable with 80% power depends on the proportion observed in the intervention group. If adherence is only 20% in the intervention group, then we can detect as different rates among the control group of 8.8-10.1%, depending on ICC. These rates are both lower than we anticipate for the intervention group and considerably higher than we expect in the control group. Assuming 200 participants per group we will have 80% power using 2-sided t-tests to detect differences of 0.28-0.32 standard deviations for continuous outcomes. Using variance estimates from Encourage data for change in the Diabetes Distress Score, another validated psychometric instrument, this translates into detecting differences as small as 3.7-4.4% of the range. Similarly, detectable differences for change in A1c are in a clinically meaningful range from 0.41-0.48%. We anticipate detectable differences for systolic blood pressure of 3-4 mmHg, and for LDL-cholesterol of 6.7-8.1 mg/dL.

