The primary analysis will test the hypothesis that medication adherence treated as a binary outcome will be greater in the treatment arm than the control arm at follow-up. As above, the primary unadjusted hypothesis test will use either a  $X^2$  test or logistic regression with GEE depending on the magnitude of observed ICCs. Statistical significance will be judged by  $p < 0.05$  for either the  $X^2$  test or the coefficient for study group in regression models. The intervention group will be compared to the control group; further analyses will use logistic regression with GEE to model adjusting for any covariates that were imbalanced between groups at baseline, and will then proceed to examine regression models adjusted for the covariates described in Table 6.

Analysis for A1c, blood pressure and LDL-cholesterol and the secondary outcomes will be very similar to the analysis of medication adherence described above. We note that we will also be able to analyze adherence as a continuous outcome as a secondary analysis using the following approach. For each of these continuous or ordinal measures, we will begin by calculating the change from baseline to 6-month follow-up for each participant. These change scores will be the units of analysis and we hypothesize greater change among the intervention groups compared to the control group. We will proceed to examine summary statistics, histograms, and scatter plots of the measured outcomes for outliers and data trends. We will then test for unadjusted differences in changes between the intervention and control groups using t-tests, Mann-Whitney-Wilcoxon tests, or regression models with GEE to account for clustering, as appropriate for the variable and ICC. Similar to above, we will then proceed with more sophisticated analyses in stages, first adjusting for baseline values of outcome variables, then for any factors that were imbalanced at baseline and finally adjusting for covariates mentioned above.

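### Towns are randomised within region-by-size strata, but no visible model includes the strata; adding them is a cheap gain in power, not the repair of a shortfall

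*Combined protocol and SAP*

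**What the plan says.** **Allocation.** Towns are the units, randomised in blocks. The Randomization section states: "We will group towns by size (small and not small) within each of the 4 regions, resulting in 8 strata". It aims for at least 3 towns in each stratum.

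**Analysis.** For adherence, the Data Analysis section says "the primary unadjusted hypothesis test will use either a" chi-square test or a logistic GEE, depending on the observed ICC. For the continuous outcomes it says: "We will then test for unadjusted differences in changes between the intervention and control groups using t-tests", with Mann-Whitney-Wilcoxon tests or GEE regression as alternatives. GEE is used when an outcome's ICC is significantly non-zero or its estimate exceeds 0.01; otherwise the simple tests apply.

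Adjusted models come afterwards. They bring in baseline values (continuous outcomes), covariates found imbalanced at baseline, and then the covariates of a Table 6 that is not in the available text. No visible sentence names region, town size or stratum as a model term, and the list under Additional Measures has neither.

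**Power.** The Power Calculations section inflates variance for towns only: "at least 80 clusters, corresponding to an average of 6-8 participants per cluster, with ICC=0.01 and 0.05 yielding" design effects of 1.084 and 1.419. It concludes: "Assuming 200 participants per group we will have 80% power using 2-sided t-tests to detect differences of 0.28-0.32 standard deviations for continuous outcomes".

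**The concern.** Stratified allocation balances the arms on region and town size. If those factors predict outcome, balancing them lowers the true sampling variance of the treatment difference. A clustered analysis without stratum terms still counts the between-stratum variation as error. Its standard error is then larger than the design warrants, its type I error falls below 5%, and it has less power than the same data could give.

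The later models are unlikely to recover this. They follow the primary test, and their first selection rule for covariates is baseline imbalance, which tends to pass over factors balanced by design. At stake is some sensitivity for adherence, A1c, blood pressure and LDL-cholesterol. Validity in the direction of false positives is not at stake here.

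**Working it through.** **Inputs from the documents.** Two-sided alpha 0.05 and 80% power. 500 recruited and two arms: "we will recruit 500 individuals with diabetes who report medication nonadherence, group randomize them to one of the 2 trial arms". Attrition: "we assume 20% attrition here, leaving 200 participants per group". At least 80 towns, stated average 6-8 participants per town; 400 completers over 80 towns is 5 per town, so m = 5-8 is used. Planning ICC 0.01-0.05; Encourage ICCs 0.001-0.015 for most measures.

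**Input not in the documents.** R, the share of between-town variance explained by the 8 strata. It is varied from 0 to 1.

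**Step 1: the plan's own figure.** With D = 1 + ICC(m - 1), the detectable difference is (1.960 + 0.842) x sqrt(2D/200) = 0.280 x sqrt(D).
- Stated D of 1.084 and 1.419: 0.292 and 0.334 SD, against the stated 0.28 and 0.32.
- m = 6 at ICC 0.01 (D = 1.05) and m = 8 at ICC 0.05 (D = 1.35): 0.287 and 0.326 SD.

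The stated figures are not exactly reproduced. The stated D values imply m of about 9.4, since (1.084 - 1)/0.01 + 1 = 9.4. That is a separate matter. What counts here is that the calculation contains no stratification term.

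**Step 2: add the strata.** Removing the stratum part of the clustering gives D_adj = m x ICC x (1 - R) + (1 - ICC). The standard error shrinks by the factor q = sqrt(D_adj/D). At the effect for which the plan has 80% power:
- power with strata = Phi(2.802/q - 1.960)
- power without strata, same stratified design = Phi(2.802/q - 1.960/q)
- type I error without strata = 2 x [1 - Phi(1.960/q)]

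Example, m = 5, ICC 0.05, R = 0.5: D = 1.20; D_adj = 0.125 + 0.95 = 1.075; q = 0.946. Power is 84.1% with strata and 81.3% without; type I error without strata is 3.8%.

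| ICC | R | SE reduction, m 5-8 | Power with strata | Power without | Forgone (points) |
|---|---|---|---|---|---|
| 0.001 | 1 | 0.2-0.4% | 80.2-80.3% | 80.1% | under 0.5 |
| 0.01 | 0.5 | 1.2-1.9% | 80.9-81.5% | 80.3-80.5% | 0.6-1.0 |
| 0.01 | 1 | 2.4-3.8% | 81.9-83.0% | 80.6-80.9% | 1.3-2.1 |
| 0.015 | 0.5 | 1.8-2.8% | 81.4-82.1% | 80.4-80.7% | 1.0-1.4 |
| 0.015 | 1 | 3.6-5.6% | 82.8-84.3% | 80.9-81.4% | 1.9-2.9 |
| 0.05 | 0.5 | 5.4-7.7% | 84.1-85.9% | 81.3-81.9% | 2.8-4.0 |
| 0.05 | 1 | 11.0-16.1% | 88.3-91.6% | 82.8-84.2% | 5.5-7.4 |

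R = 1 is a ceiling. At R = 0 nothing is forgone.

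**Step 3: simulation.** All runs use 80 towns, 10 per stratum, and a normal outcome.
- Equal towns of 5 completers, ICC 0.05, R = 0.5: type I error 4.1% and power 80.9% without strata, 5.1% and 83.2% with.
- Same, R = 1: 3.0% and 81.6% without, 4.9% and 86.8% with.
- Unequal towns (size CV 0.7), 400 analysed, corrected standard error, difference 0.32 SD, total ICC 0.015, R = 0.5: power 84.4% without, 85.2% with.
- Same, R = 0: 86.5% without, 85.0% with. Adjustment is then slightly costly.
- With stratum terms and an uncorrected sandwich standard error, type I error was about 7-9%.

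**Step 4: the branch that ignores towns.** A chi-square or t test has type I error 2 x [1 - Phi(1.960/sqrt(D))], leaving aside any stratum gain. At ICC 0.01 and m = 5-8 this is 5.5-5.8%. If the true ICC is 0.05 but the estimate falls below the trigger, it is 7.4-9.2%.

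**The case against.** The case against acting on this is substantial.

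- **The effect may be negligible.** A town ICC from a model without strata already contains stratum variation. At the Encourage values the gain is at most about 3 points, and less in simulation. This stands, with one caveat: Encourage covered two regions and this trial adds two more.
- **Change scores.** Outcomes other than binary adherence are analysed as change from baseline, which removes fixed regional differences in level. R may therefore be small for them. This stands.
- **The primary outcome is binary.** The calculations use a normal outcome. In a logistic model, stratum terms change the odds ratio from marginal to conditional, so the narrowing of the standard error does not carry over; the benefit is in power. This stands.
- **Table 6 cannot be seen** and may list region. True, but the primary test would remain unadjusted.

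A reader might infer that the trial loses power it was counting on. The power section does not support that: it credits nothing to stratification, and at its own effect size the unadjusted test keeps 80% or slightly more. A reader might also infer that intervals are too wide throughout. That holds only where clustering is modelled and the strata are prognostic; in the branch that ignores towns the error can run the other way. Larger losses can be produced by letting the strata alone carry 10% of outcome variance, but that puts total clustering above the plan's upper ICC of 0.05, and nothing in the documents supports it.

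**Conclusion.** The omission is real: allocation uses eight strata, the main tests are unadjusted, and no visible model contains the strata. Confidence in that is high.

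Its size is modest and less certain (medium confidence). When town clustering is accounted for, the forgone power is about 0-3 points at ICC 0.001-0.015. It is about 2-7 points at ICC 0.05 if the strata explain at least half of between-town variance. That share is assumed. Table 1 shows the target counties differing in diabetes prevalence (11.7-17.5%) and primary care providers (1.5-10.1 per 10,000), so prognostic strata are plausible but not shown. This is a cheap improvement, and the planned 80% power does not depend on it.

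**What to change.** In the Data Analysis section, prespecify for each outcome one primary model that always accounts for town clustering and includes region and town size as fixed main effects (3 + 1 = 4 degrees of freedom). Use logistic regression for adherence and linear regression for A1c, blood pressure and LDL-cholesterol. If the eight strata are preferred (7 degrees of freedom), state a rule for combining sparse ones, since a stratum may hold only 3 towns. Use a small-sample-corrected robust standard error, such as Kauermann-Carroll, with a t reference on towns minus parameters. Keep the unadjusted comparison as descriptive.

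**Cost.** No new data: a short paragraph and 4-7 of about 78 degrees of freedom. The correction is part of the change, because stratum terms with an uncorrected standard error inflate type I error. The adherence odds ratio becomes conditional on the strata and should be labelled so. If the strata prove unrelated to outcome, there is a slight loss of power.
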